### **12.3 Baseline/Procedure**

Subjects should undergo the baseline procedure within approximately 30 days from signing the ICF. Final eligibility requirements will be assessed at the baseline visit. Subjects will undergo a baseline endoscopic examination, including grading prior to any surgical procedure(s). Video endoscopy capture is required, pictures are optional. Subjects will also undergo baseline assessments such as SNOT-22, RSI, and CRS side-specific symptom questionnaire before any surgical procedures.

- Female subjects of childbearing potential will need to confirm not pregnant or nursing prior to the baseline procedure per site standards.
- Subject preparation for baseline procedure
- Subjects will be prepared for the baseline procedure per standard investigator protocol used for nasal endoscopy and procedures.
- The anesthesia period should be as long as necessary to ensure complete numbness of the subject's septum and middle turbinate. Once properly anesthetized, subjects will undergo the baseline procedure.

#### **12.3.1 Bilateral Frontal SBD**

Confirm bilateral FSO access and complete bilateral in-office dilation per the Cube Navigation System, VenSure™ Nav Balloon Device, and Inflation Device IFUs. If the eligibility CT Scan does not meet the Cube Navigation System requirements, the CT Scan may need to be re-done.

Subjects may be asked to take off their mask (just like earrings, glasses, etc.,) for the few seconds during which the CT scan is captured to maximize accuracy with the navigation system.

Prior to implant placement:

- Confirm successful bilateral frontal SBD with an opening amendable for PROPEL Contour placement on each side.
- Evaluate final subject eligibility by confirming that the subject's anatomy and overall condition is appropriate for PROPEL Contour placement.

### **12.3.2     Optional In-office Procedures**

If clinically necessary, in-office sinus surgical procedures (e.g., inferior turbinate reduction, concha bullosa treatment) may be performed according to standard of care at the baseline visit prior to randomization. Traditional surgical septoplasty for inferior septal deviation such as bone spur on maxillary crest may be performed. Packing such as Merocel may be placed in the nasal or ethmoid cavity, if necessary. These procedures should be performed bilaterally on each side of the sinuses.

If clinically necessary, bilateral dilation of the maxillary or sphenoid sinuses may be performed using the study devices (i.e., Cube Navigation System, VenSure Nav Balloon Device) after completing bilateral frontal BSD of the FSO. Alternatively, the investigator may use a commercially available balloon dilation device to dilate the maxillary, sphenoid sinuses or eustachian tubes.

Septoplasty ballooning and ethmoidectomy (anterior, posterior, total) are not permitted at the baseline visit prior to randomization. Polypectomy of nasal polyps extending beyond the middle meatus (grade >2) is not permitted. Draf I, Draf II a/b, Draf III or any other procedures involving cutting to the frontal sinuses are not permitted. No use of steroid soaked packing materials is permitted.

### **12.3.3     Randomization**

Subjects meeting final eligibility and undergoing the successful completion of bilateral frontal BSD will be randomized using the envelop method to receive 1 PROPEL Contour on the treatment side.

### **12.3.4     Implant Placement**

PROPEL Contour is provided by sponsor and must be placed by trained PIs according to the IFU. No hemostatic packing materials of any kind should be placed within the implants unless medically necessary. Packing such as the Merocel tampon may be placed in the nasal or ethmoid cavity, if necessary. No other packing materials or interventions containing steroids of any kind should be placed in any other sinus.

- Record video and perform endoscopy of post-procedure anatomy, including adequate view of the frontal sinus recess implant deployment and final implant placement; and
- Record the implant apposition on the CRF.

The study treatment phase begins upon introduction of the PROPEL Contour Sinus Implant delivery system into the study subject after successful bilateral balloon dilation of the FSO.

The PROPEL Contour Sinus Implant delivery system should be disposed per standard institutional practices for biohazard waste.

If the sinus implant, implant delivery system, VenSure Nav Balloon Device, Inflation Device, or other components are associated with a device-related AE, deficiency, malfunction or failure, the impacted device or its parts should be returned to sponsor for evaluation, if possible. For the return of biohazard product, sponsor must be contacted prior to product return for handling instructions.

## **12.4 Follow-Up**

The follow-up period begins immediately post-treatment (once the study implant is placed in the subject in the clinical investigator's office).

At each follow-up visit, the subject will undergo endoscopic evaluation with grading and video recording at Day 21, 45, 90 and 180 (end of study). After suctioning, endoscopic grading is performed and recorded on the endoscopic assessment CRFs. Suctioning and clearing mucous/stent debris of the FSO should be completed prior to Day 45 CT scan. It is preferred that the PROPEL Contour Sinus Implant be left in place for 30 days but can be removed at investigator discretion.

An overview of the assessments to be performed at each follow-up interval along with required timing is provided in Section 7.

A CT scan is repeated at Day 45 (primary endpoint) and again at Day 180. The acquisition and measurements by the centralized imaging core lab are detailed in Section 13.

## **12.5 Unscheduled Visits**

Subjects may come in for additional unscheduled office visits if necessary. Circumstances that may warrant additional visits include but are not limited to:

- Worsening of sinus symptoms, and/or
- Sinus-related adverse events requiring medical evaluation.

The assessment at an unscheduled visit may consist of:

- Endoscopic evaluation with grading and video recording; and.
- SNOT-22, RSI and site-specific symptom questionnaires.

## 13 CT SCAN AND PRODUCT ACCOUNTABILITY

### 13.1 Image Acquisition

The screening CT scan must be performed  $\leq$  90 days prior to the baseline procedure to confirm the diagnosis of CRS after a period of appropriate medical therapy and prior to making a recommendation for BSD. The follow-up CT at Day 45 and 180 shall be performed after endoscopic evaluation and debridement to ensure no implant remnants are present on the scan to ensure blinded review.

The subject needs to be in seated position with the chin in a chin rest for imaging to occur. The cone-beam CT scan window must encompass the frontal, ethmoid, maxillary and sphenoid sinuses and OMC on both sides in the axial, coronal and sagittal planes.

### 13.2 Centralized Blinded Review

The primary efficacy endpoint requires precise measurements of the FSO using reconstructed cone beam images in the axial, coronal and sagittal planes. The image reconstructions and measurements of CT-related endpoints will be performed by board-certified independent radiologists at the centralized imaging core lab in accordance with the standardized protocol (see CP-00038). The reviewers will be blinded to treatment assignment and have no access to any symptomatic or endoscopic outcomes.

### 13.3 Product Accountability

An appropriate number of EXPAND study devices including Inflation Device will be provided to the study sites. The sites maintain the EXPAND study devices in a locked, secure location. Only clinical investigators participating in the study will have access to the EXPAND study devices. Dispensing of EXPAND study devices will be documented by authorized personnel. Each batch of the PROPEL Contour Sinus Implant, VenSure Nav Balloon Device and Inflation Device will be tracked by the unique device identifier.

EXPAND study devices including the unique device identifier received by the clinical site will be logged in by the site personnel on inventory logs and/or the EDC system. Final reconciliation will be completed at each site before or during site closure. Any unused inventory and Cube Navigation System will be returned to the sponsor at the direction of the sponsor or at the close of the study. At the end of the study, overall study final device reconciliation will be completed internally by the sponsor.

## 14 PRIOR AND CONCOMITANT MEDICATIONS

The following medication is allowed *prior* to and *post*-baseline procedure:

- INCS sprays prior to and post, starting after 7 days
- Orally inhaled steroids for control of asthma; and

- Stable regimens of leukotriene inhibitors and/or immunotherapy for allergies

The following medication is not allowed *prior* to the baseline procedure:

- A 30-day restriction for use of parenteral and injected steroids (e.g., Kenalog)
- A 14-day restriction for use of oral steroids, budesonide and/or any other sinus steroid irrigations/rinses or drops, nebulized steroids administered nasally; and
- A 45-day restriction for biologics for CRS treatment (such as Dupixent).

The following medication is allowed *post*-baseline procedure:

- Daily use of saline sprays/rinses/irrigations in both sinuses from Day 1
- Antibiotics if infection is suspected at any time during the study; and
- INCS sprays (excluding Xhance) in one or both sinuses starting after 7 days as clinically necessary.

The following medication not allowed *post*-baseline procedure:

- Other corticosteroids (e.g., oral, parenteral, injections, budesonide or other sinus steroid irrigations/rinses or drops, breath powered Xhance, nebulized steroids administered nasally or other drug eluting stents) through Day 45, unless clinically necessary, to ensure unbiased assessment of the primary endpoint; and
- Biologics for CRS treatment (e.g., Dupixent).

## **15 MEDICAL AND SURGICAL INTERVENTIONS**

Subsections below describe the rescue treatments consisting of medical and surgical interventions that will be allowed during the study follow-up based upon subject's symptomatic and endoscopic outcomes.

### **15.1 Medical Intervention**

During study follow-up, INCS sprays (excluding Xhance) will be allowed starting after Day 7 visit, if clinically necessary.

Other corticosteroids (e.g., oral, parenteral, injections, budesonide or other sinus steroid irrigations/rinses or drops, breath powered Xhance, nebulized steroids administered nasally or other drug eluting stents) are not allowed through Day 45, unless there is a clinically significant increase or persistence in frontal sinus inflammation, coupled with subject complaint of sinusitis symptoms that cause subject to request medical intervention.

### **15.2 Surgical Intervention**

Surgical intervention (e.g., repeat balloon dilation or sinus surgery, in-office polypectomy) may be required in cases where a clinically significant increase or persistence in frontal sinus

inflammation occurs, coupled with complaints of sinusitis symptoms that cause subject to prefer a surgical intervention (e.g., sinus surgery).

All medical and surgical interventions will be noted on the concomitant medication and follow up CRFs.

## 16 ASSESSMENT OF SAFETY

### 16.1 Specification of Safety Parameters

Adverse events (AE) for each subject from the time the subject gives written informed consent (enrollment) through Day 180 (end of study) will be recorded in the EDC system and monitored. Each AE will be evaluated by clinical investigators in terms of severity (i.e., mild, moderate, severe) as well as strength of relationship (i.e., not related, unlikely related, probably related, definitely related, indeterminate) to the study drug (mometasone furoate), study devices, and procedures (BSD, implant placement). Each AE will be reviewed by sponsor in accordance with sponsor's SOP. The study sponsor is responsible for ensuring that all AEs are appropriately recorded, adjudicated and, when applicable, reported to the government(s), ethics committee(s) and other study centers per applicable regulations.

Subjects with CRS experience a persisting set of symptoms associated with the disease and may continue to present with a wide range of symptoms during the recovery process after in-office balloon dilation. These may include symptoms such as pain and discomfort, headache, decreased sense of smell, crusting, epistaxis, and other symptoms. Patients healing appropriately after in-office procedure may suffer from acute infections and/or inflammatory exacerbations unrelated to the procedure due to the natural course of their CRS. Therefore, clinical investigators will evaluate the occurrence of AEs excluding usual post-operative recovery signs and symptoms experienced by study subjects, unless corroborated by objective findings and/or requiring specific medical or therapeutic interventions (e.g., antibiotics, repeat ESS).

Note: The need for medical or surgical intervention in the FSO post-dilation that is captured on the endoscopic assessment CRF will not be considered as an AE. Likewise, other endoscopic findings such as inflammation, adhesion/scarring, and edema of the FSO will not be considered as AEs.

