## 4 DEFINITIONS OF TERMS

Term	Definition
Adhesion/scarring grading scale for the ethmoid sinus	
Adhesion/scarring severity in the ethmoid sinus graded on a 5-point scale as follows:
 

• 0: None

• 1: Small but non-obstructing (no separation required)

• 2: Obstructing, but easily separated

• 3: Dense and obstructing, separation difficult

• 4: Severe: complete adhesion of the middle turbinate to the lateral nasal wall

Adhesion/scarring grading scale for the frontal sinus ostium/ostia (FSO)	
Adhesion/scarring in the FSO assessed on a 4-point scale as follows:
 

• 0: No visible granulation/scarring in the FSO

• 1: Minimal amount of granulation, scarring or contraction observed but not obstructing the FSO (intervention not warranted)

• 2: Moderate amount of obstructive granulation, scarring or contraction present in the FSO (intervention is warranted)

• 3: Significant amount of scarring or contraction causing obstruction of the FSO requiring intervention (likely to compromise patency if not removed)

Adverse device effect (ADE)	
Adverse event related to the use of an investigational medical device. This definition includes adverse events resulting from insufficient or inadequate instructions for use, deployment, implantation, installation, or operation, or any malfunction of the investigational medical device. This definition also includes any event resulting from use error or from intentional misuse of the investigational medical device. If a comparator medical device is used in the investigation, this definition also applies to ADEs of the comparator device. [ISO 14155:2020]

Adverse event (AE)	
Any untoward medical occurrence, unintended disease or injury, or untoward clinical sign(s) (including abnormal laboratory findings) in subjects, users or other persons, whether or not related to the investigational medical device and whether anticipated or unanticipated. This definition includes events related to the procedures involved. This definition also includes events related to the investigational medical device or any comparator device. For users or other persons, this definition is restricted to events related to the use of investigational medical devices or comparators. [ISO 14155:2020]

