Serious adverse event (SAE)	
Adverse events are considered "serious" if, in the view of either the investigator or sponsor, they result in any the following outcomes:
 
 
• Death; or
 
• A life-threatening illness or injury; or
 
• Permanent impairment of a body structure or a body function; or
 

	

• Inpatient hospitalization or prolongation of existing hospitalization; or

• Medical or surgical intervention to prevent life-threatening illness or injury or permanent impairment to a body structure or a body function; or

• Fetal distress, fetal death, or a congenital anomaly/birth defect.

 
Important medical events that may not result in death, be life-threatening, or require hospitalization may be considered serious when, based upon appropriate medical judgment, they may jeopardize the patient and may require medical or surgical intervention to prevent one of the outcomes listed in this definition.
 
Planned hospitalization for a pre-existing condition, or a procedure required by the CIP/CSP, without serious deterioration in health, is not considered a serious adverse event. [ISO 14155:2020]

Sino-Nasal Outcome Test (SNOT-22)	Validated, disease-specific, symptom-scoring instrument consisting of 22 questions, each scored by patient on a 6-point scale as follows: 

• 0: No problem

• 1: Very mild problem

• 2: Mild or slight problem

• 3: Moderate problem

• 4: Severe problem

• 5: Problem as bad as it can be

 The maximum total score for all symptoms is equal to 110.
Source data	All information in original records and certified copies of original records of clinical findings, observations, or other activities in a clinical trial necessary for the reconstruction and evaluation of the trial.
Source documents	Original documents, data, and records. Printed, optical, or electronic documents containing source data.
Subject	An individual who participates in a clinical investigation

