## 9.2 Secondary Endpoints

- CT grading by an independent, blinded reviewer (Day 45, 180):
  - Cross-sectional area of FSO (Day 180 only)
  - FSO minimum diameter
  - FSOT volume
  - Zinreich's modified Lund-Mackay score for the frontal sinus
  - Lund-Mackay score for the frontal sinus
- CT grading by clinical investigators (Day 45, 180):
  - Lund-Mackay score for the frontal sinus
- Need for post-operative intervention as determined by clinical investigators based on endoscopic evaluation (Day 21, 45, 90, 180):
  - Repeat frontal SBD warranted or performed for restenosis/occlusion in the frontal recess/FSO; or
  - Surgical intervention warranted or performed to debride obstructive adhesions/scarring or for restenosis/occlusion in the frontal recess/FSO; or
  - Oral steroids warranted or prescribed to resolve recurrent edema in the frontal recess/FSO
- Endoscopic grading by clinical investigators (Day 21, 45, 90, 180):
  - Adhesion/scarring grade in the frontal recess/FSO and ethmoid sinus
  - Inflammation score in the frontal recess/FSO
  - Polypoid edema in the frontal recess/FSO
  - Polyp grade in the ethmoid sinus
- Patient-reported outcomes:
  - CRS side-specific symptom score (Day 21, 45, 90, 180)
  - SNOT-22 score (Day 180)
  - RSI score (Day 180)
- Implant delivery success rate by clinical investigators

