### 16.4 Guidelines for AE Reporting

All AEs, regardless of seriousness or relationship to the study devices, will be recorded in the EDC system and will include event description, date of onset, investigator's assessment of severity, relationship to study devices, and date of resolution/stabilization of the event. All AEs occurring while on study must be documented appropriately regardless of relationship. All AEs will be followed through end of the study.

Any pre-existing medical condition that is present at the time of screening will not be reported as an AE. The occurrence of diagnostic or elective surgical procedures for a pre-existing condition will not be recorded as an AE, unless the condition becomes more severe or results in an AE.

Whenever possible, diagnosis or single syndrome should be reported instead of symptoms. The investigator should specify the date of onset, severity, action taken with respect to the study device(s), corrective treatment/therapy given, additional investigations performed, outcome, and his/her opinion as to whether there is a reasonable possibility that the AE was caused by the study device(s).

The investigator should take appropriate measures to follow all AEs until resolution or until progression has been stabilized, or until study exit, to ensure the safety of the subjects. If the AE continues beyond the last planned visit per protocol and/or the subject withdraws from the study, clinical investigators should follow the subjects according to standard of care.

If a subject decides to withdraw from the study, clinical investigator should follow patients with ongoing AEs till resolution according to the standard of care.

An investigator will submit to the sponsor a report of AEs occurring during this investigation as defined in the table below.

Type of Report	Submission Schedule
Device-related AE	Verbal report or initial entry into the AE CRF within 24 hours from assessment followed by written report within 10 working days
Subject Death	Verbal report within 24 hours followed by a written report within 2 working days
SAE/SADE/UADE/US ADE	Verbal report within 24 hours followed by a written report within 5 working days

The investigator will report the above to the reviewing IRB per the IRB's guidelines. The study sponsor will be responsible for reporting safety events to the Food and Drug Administration (FDA) as required per 21 CFR 812 and 21 CFR 803.

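### The Note in Protocol 16.1 takes FSO interventions and endoscopic findings out of AE status with no exception for serious cases, so an event meeting a Section 4 SAE outcome could miss the SAE route

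*Protocol*

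**What the plan says.** Protocol 16.1 closes with a Note containing two exclusions. First, the need for medical or surgical intervention in the FSO after dilation, when "captured on the endoscopic assessment CRF will not be considered as an AE". Second, "other endoscopic findings such as inflammation, adhesion/scarring, and edema of the FSO will not be considered as AEs". Neither sentence excepts events that are serious.

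The sentence before the Note treats a different group, the usual signs and symptoms of recovery. These are not counted as AEs "unless corroborated by objective findings and/or requiring specific medical or therapeutic interventions (e.g., antibiotics, repeat ESS"). That exception is attached to recovery symptoms and is not repeated in the Note.

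Protocol Section 4 defines an AE broadly, as any untoward medical occurrence, whether or not device-related and including events related to the procedures. An AE is serious if it results in one of the listed outcomes. Two of these matter here: "Inpatient hospitalization or prolongation of existing hospitalization" and "Medical or surgical intervention to prevent life-threatening illness or injury or permanent impairment to a body structure or a body function".

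For SAE, SADE, UADE and USADE, the table in Protocol 16.4 requires: "Verbal report within 24 hours followed by a written report within 5 working days".

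**The concern.** Keeping routine efficacy events out of the AE count is common and sensible. In this trial the need for post-operative intervention and the endoscopic grades are secondary endpoints, and reporting each one again as an AE would add paperwork without information. The Note goes further, because it sets no upper limit on seriousness. The excluded group includes operations that were actually carried out: one component of the endpoint in Protocol 9.2 is "Surgical intervention warranted or performed to debride obstructive adhesions/scarring or for restenosis/occlusion in the frontal recess/FSO". Grade 3 on the Section 4 scarring scale for the FSO describes obstruction that requires intervention.

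At stake are the safety functions that hang on AE status: a prompt report to the sponsor, a causality judgement, an expectedness judgement and a place in the SAE tables. The excluded events are tissue responses at the site of the implant, so they are the ones for which a causality judgement would be most informative.

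**Working it through.** No arithmetic applies, and the plan has no figure to reproduce. The check is to follow one event through the text.

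**Test event.** FSO scarring or restenosis is seen at endoscopy and recorded on the endoscopic assessment CRF. Intervention is needed, and the subject has an unplanned admission.

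1. **AE definition (Protocol Section 4).** This is an untoward medical occurrence, so it is an AE.
2. **Note (Protocol 16.1).** The need for intervention is not an AE under the first exclusion. The scarring is not an AE under the second. The admission is an outcome and not an event in its own right, so it has to attach to some AE. Steps 1 and 2 contradict each other.
3. **SAE definition (Section 4).** The outcome criteria are met, but the entry applies them to adverse events. If step 2 governs, the event is not an SAE. ADE is also defined through adverse event, and SADE and USADE through ADE, so these close as well.
4. **Causality (Protocol 16.2.2).** The relationship is graded for each AE. If step 2 governs, no grade is required.
5. **Expectedness (16.2.3) and sponsor review (16.3).** The first covers device-related AEs and the second covers AEs. Neither is triggered.
6. **Reporting table (16.4).** The table has three rows: device-related AEs, subject deaths, and SAE/SADE/UADE/USADE. Only the death row is independent of all the classifications above. The UADE part of the third row is taken up under the objection.
7. **Safety tables (SAP 9.7).** These count AEs, SAEs and device effects. The section contains no exclusion of its own; the event is absent only because it was never classed as an AE upstream.

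**What still captures the event.** Interventions are noted on the concomitant medication and follow-up CRFs (Protocol 15.2) and counted in the secondary endpoint (SAP 9.2.3). Hospitalizations are a health-economic measure (Protocol 9.5, SAP 9.8), analysed in the PTE population (SAP Table 2). The data are therefore kept, but none of these routes carries a causality assessment or a reporting deadline.

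**Tension inside 16.1.** The sentence before the Note keeps recovery symptoms as AEs when they require intervention, and repeat ESS is one of its examples. Protocol 15.2 couples surgical intervention with complaints of sinusitis symptoms. The same symptomatic episode can thus be an AE under that sentence and not an AE under the Note, and two sites could classify it differently.

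**The case against.** A reader might infer that no FSO event, however serious, can ever enter the safety route. The documents do not support that, for these reasons.

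- **Scope.** The Note covers the need for FSO intervention captured on one CRF, and endoscopic findings of the FSO. Separate complications such as infection or cerebrospinal fluid leak, and deaths, remain reportable.
- **A second route.** Under the sentence before the Note, a symptomatic subject who has revision surgery can be reported as an AE, and so as an SAE. The Note makes this uncertain but does not rule it out.
- **UADE.** The Section 4 definition speaks of serious adverse effects and unanticipated serious problems associated with a device, and does not pass through AE. An unanticipated serious device effect therefore stays reportable. Scarring, adhesion and restenosis are not named in the Section 17.1 risk list, so such an event might even qualify.
- **Planned admission.** Section 4 says that planned hospitalization for a pre-existing condition, without serious deterioration in health, is not an SAE. Protocol 16.4 treats elective procedures for pre-existing conditions similarly unless the condition worsens or an AE results. A revision with a planned admission would often fall there.
- **Relatedness is not seriousness.** Scarring judged to be caused by the implant meets no SAE outcome by that fact alone.
- **Other duties.** Section 16.4 separately states the sponsor's regulatory reporting responsibility.

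All of this stands and narrows the point. It does not supply the missing exception. An anticipated serious FSO event, with an unplanned admission or an intervention to prevent permanent impairment, still has no assured path to an SAE report.

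**Conclusion.** The point holds in a limited form. Read literally, the Note in Protocol 16.1 allows an FSO event that meets an SAE outcome in Section 4 to escape SAE/SADE classification, causality grading, the 24-hour report and the SAE tables. It conflicts with the Section 4 definitions and sits uneasily with the sentence before it. The right word is could: a careful site may report the event anyway.

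The size cannot be calculated, because the documents give no rate of serious FSO events. With 80 randomized subjects in an office-based, post-market study, few are likely; that is a judgement, not a figure from the plan. The conclusion rests on taking the Note at its word, as a site working from the Protocol would have to. Efficacy conclusions are not affected.

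A reader might also infer that every device-related FSO finding should become an AE. The documents do not make that case. Under Protocol 19.3 the treating investigators are unblinded, and only one side carries an implant, so non-serious endpoint findings could be attributed to the device on one side only.

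**What to change.** Reconcile the Note in Protocol 16.1 with the AE and SAE definitions in Section 4 and the reporting table in 16.4. A clause at the end of the Note, applying to both exclusions, is enough: *unless the event meets the SAE definition in Section 4, in which case it is also reported as an AE/SAE and assessed for causality.*

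Routine non-serious endpoint events stay excluded. SAP 9.7 needs no change, since its tables will pick up the events once they are classed as AEs.

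The cost is one clause in the Protocol and a few more AE forms. The affected events will appear in both the efficacy and the safety tables, and the report should say so to prevent them being read as separate events.
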